6.2 Treatment Regimens

Patients should receive nivolumab at a dose of 3 mg/kg as a 60-minute IV infusion, on Day 1 of each treatment cycle every 2 weeks for 24 weeks or until progression, unacceptable toxicity, withdrawal of consent, or the study ends, whichever occurs first. Patients should begin study treatment within 3 calendar days of enrollment.

Dosing calculations should be based on the body weight assessed at baseline. It is not necessary to re-calculate subsequent doses if the participant weight is within 10% of the weight used to calculate the previous dose. All doses should be rounded up or to the nearest milligram per institutional standard.

6.3 Populations for Analyses

The following subject populations will be considered in this trial:

- **All Enrolled Patients:** All patients who signed an informed consent form and were registered into the IVRS.
- **All Treated Patients:** All Patients who received any nivolumab. This is the primary population for safety analyses. Subpopulation analyses will be conducted by tumor type.

7 STATISTICAL ANALYSES

7.1 General Methods

Unless otherwise noted, discrete variables will be tabulated by the frequency and proportion of subjects falling into each category, grouped by tumor type. Percentages given in these tables will be rounded to the first decimal and, therefore, may not always sum to 100%. Percentages less than 0.1 will be indicated as '< 0.1'. Continuous variables will be summarized by tumor type using the mean, standard deviation, median, minimum, and maximum values.

The conventions to be used for imputing partial dates for analyses requiring dates are described in Section 8.

Unless specified otherwise, all analyses will be tabulated in 3 columns: NSCLC, RCC, and the 2 cancer types pooled.

7.2 Study Conduct

Unless otherwise specified, the study conduct data will be presented on all treated subjects by tumor type.

7.2.1 Relevant Protocol Deviations

All protocol deviations identified will be summarized by protocol deviation type for all treated subjects.

The following programmable deviations from inclusion and exclusion criteria will be considered as relevant protocol deviations. Non-programmable relevant eligibility and on-treatment protocol deviations, as well as significant (both programmable and non-programmable) eligibility and on-treatment protocol deviations will be reported through ICOMaster.

A by-subject listing will be provided.

7.3 Study Population

Unless otherwise specified, the study population data will be presented on all treated subjects by tumor type.

7.3.1 Subject Disposition

The total number of subjects enrolled, treated and not treated will be presented along with the reason for not being treated.

In addition, the below summary will be provided.

- **Pre-Treatment Status:** The total number of subjects entered into the treatment phase and not entering the treatment phase will be presented along with the primary reason for not entering the treatment phase of this study.
- **Subject Status (End of Treatment):** Total number of subjects completed the phase of study-treatment along with the primary reason for not completing this phase of the study or not continuing in the treatment period of the study will be presented.
- **Subject Status (End of Study):** Total number of subjects continues to be followed (Yes/No) and primary reason for not continuing in the study will be presented.

Also, total number of subjects by investigational site will be provided.

A by subject listing of pre-treatment, end of treatment and end of study status will be provided separately.

7.3.2 Demographics and Baseline Characteristics

Overall summary of the following demographic and baseline characteristics will be summarized for all treated subjects and also by tumor type.

- Age
- Age Category (< 65, ≥ 65 - <75, ≥ 75years)
- Gender
- Race
- Smoking history by Status: Never/Current/Former/Unknown
- Initial disease diagnosis
 - Time from initial diagnosis to study treatment first dose
 - Tumor Type
- Current Disease Diagnosis
 - Time from diagnosis to study treatment first dose
 - Disease stage at study entry: I/II/III/IV

A by subject listing will be provided separately for demography, initial diagnosis and current disease diagnosis.

7.3.3 Physical Measurements

Descriptive statistics of the following physical measurements will be summarized for all treated subjects by tumor type and overall.

- Baseline weight (kg)
- Baseline height (cm)
- Baseline BMI (kg/m²)
- Baseline Eastern Cooperative Oncology Group (ECOG) performance status

In addition, physical measurements will also be summarized by study visit for each tumor type and overall.

A by subject listing will be provided.

7.3.4 Medical History

General medical history will be coded and grouped into Preferred Terms (PT) by System Organ Class (SOC), using Medical Dictionary for Regulatory Activities (MedDRA) version 20.1 or higher. Listings and summaries will be based on the SOCs and PTs. Summaries will be provided for all treated subjects by tumor type and overall.

A by subject listing of medical history will be provided. In addition, specific disease history will be displayed in listings.

7.3.5 Prior Therapy

Descriptive statistics of prior therapies will be summarized for all treated subjects by tumor type and overall.

- Prior Radiotherapy
 - Subjects received prior radiotherapy (yes/no)
 - Sites of radiotherapy
 - Time from therapy stop date to study treatment first dose
- Prior Surgery Related to Cancer
 - Subjects received any prior surgery related to cancer (yes/no)
 - Time from surgery to study treatment first dose
 - Type of surgery
- Prior Systemic Cancer Therapy
 - Subjects with systemic cancer therapy (yes/no)
 - Setting of regimen (adjuvant therapy/metastatic disease/neo-adjuvant therapy)
 - Duration of prior systemic cancer therapy
 - Best response to regimen (CR/PR/SD/PD/unable to determine/not applicable)
 - Primary reason regimen was discontinued
 - Time from therapy stop to study treatment first dose

A by subject listing of the above prior therapies will be provided separately.

7.3.6 Subsequent Systemic Cancer Therapy

A by-subject listing will be provided separately for subsequent systemic cancer therapy, radiotherapy for treatment of tumors and on-treatment/subsequent surgery for treatment of tumors.

7.3.7 Physical Examination

Subjects with abnormal baseline physical examination will be tabulated by examination criteria for all treated subjects by tumor type.

The number and percentage of patients reporting physical examination results (Normal/Abnormal) will be presented per body system/examination criteria per time-point for all treated subjects.

A by-subject listing will be provided.

7.3.8 Clinical Complaints

A by-subject listing will be provided.

7.3.9 Diagnostic and Medical Treatment Procedures

A by-subject listing will be provided separately for diagnostic and medical treatment procedures.

7.4 Extent of Exposure

Unless otherwise specified, the exposure data will be presented on all treated subjects by tumor type.

7.4.1 Administration of Study Therapy

The following parameters will be summarized (descriptive statistics):

- Relative dose intensity (%) using the following categories: < 50%; 50 - < 70%; 70 - < 90%; 90 - < 110%; ≥ 110%.
- Number of doses received
- Cumulative dose
- Duration of treatment

A by-subject listing of dosing of study medication (record of study medication, infusion details, and dose change) and a listing of batch number will be also provided.

Below table summarizes the key parameters used to calculate dosing data.

Table 7.4-1: Administration of Study Therapy: Definition of Parameters

Nivolumab	
Dosing schedule per protocol	3 mg/kg Q2 weeks
Cumulative Dose	Cumulative dose (mg/kg) is sum of the doses (mg/kg) administered to a subject during the treatment period
Relative dose intensity (%)	$[\text{Cumulative dose (mg/kg)} / ((\text{Last dose date} - \text{Start dose date} + 14) * 3 / 14)] \times 100$
Duration of treatment	Last dose date - Start dose date +1

7.4.2 Modifications of Study Therapy

7.4.2.1 Dose Delays

A dose will be considered as actually delayed if the delay is exceeding 3 days (i.e., greater than or equal to 4 days from scheduled dosing date). The length of dose delay is defined as (duration of previous cycle in days - 14). The Dose delays will be divided into following categories: 4 - < 8 days, 8 - < 15 days, 15 - < 43, >= 43 days. Reason for dose delay will be retrieved from CRF dosing pages.

The following parameters will be summarized by tumor type and overall:

- Number of dose delayed per subject, Length of Delay, and Reason for Dose Delay
- Number of subjects with at least one dose delayed along with reason for dose delay

7.4.2.2 Dose Modifications

There will be no dose escalations or reductions of nivolumab allowed.

Nivolumab infusion can be interrupted and/or the IV infusion rate can be reduced. This information will be retrieved from CRF dosing pages.

The following parameters will be summarized by tumor type and overall:

- Number of subjects with at least one dose infusion interrupted along with the reason for the interruptions and number of infusions interrupted per subject

A by subject listing of study drug administered will be provided. A batch listing number will be also provided.

[REDACTED]

7.5 Efficacy

Not applicable.

7.6 Safety

Unless otherwise specified, the safety data will be presented by tumor type. Data analyses will be conducted only on the safety data collected within the maximum of the 26-week study period, which will include safety collected during the follow-up of participants who discontinue treatment before 24 weeks. The post study treatment follow-up is defined as participants who discontinue study treatment before 24 weeks will be followed for 100 days after the last dose of nivolumab or for a total of 26 weeks from first on-study treatment with nivolumab whichever is earliest.

7.6.1 Deaths

Deaths will be summarized by tumor type:

- All deaths, reasons for death
- Deaths within 100 days of last dose received or for a total of 26 weeks from first on-study treatment with nivolumab whichever is earliest, reasons for death

By-subject listing of deaths will be provided for the all enrolled subjects population.

7.6.2 Serious Adverse Events

Unless for the safety window would be as the defined as in section 7.6. For participants assigned to treatment and never treated with study drug, SAEs should be collected for 30 days from the date of treatment assignment.

Serious adverse events will be summarized by tumor type:

- Overall summary of SAEs by worst CTC grade (grade 1, 2, 3, 4, 5, unknown) presented by SOC/PT
- Overall summary of drug-related SAEs by worst CTC grade (any grade, grade 3-4, grade 5) presented by SOC/PT.

The analysis will be conducted using the 100-day safety window or for a total of 26 weeks from first on-study treatment with nivolumab, whichever is earliest.

By-subject SAE listing will be provided for the all enrolled subjects population.

7.6.3 Adverse Events Leading to Discontinuation of Study Therapy

AEs leading to discontinuation will be summarized by tumor type:

- Overall summary of AEs leading to discontinuation by worst CTC grade (grade 1, 2, 3, 4, 5, unknown) presented by SOC/PT

The analysis will be conducted using the 100-day or for a total of 26 weeks from first on-study treatment with nivolumab whichever is earliest safety window.

By-subject AEs leading to discontinuation listing will be provided.

7.6.4 Adverse Events

Adverse events will be summarized by tumor type:

- Overall summary of any AEs by worst CTC grade (grade 1, 2, 3, 4, 5, unknown) presented by SOC/PT.
- Overall summary of drug-related AEs by worst CTC grade (any grade, grade 3-4, grade 5) presented by SOC/PT.

By-subject AE listing will be provided.

7.6.5 Select Adverse Events

Unless otherwise specified, analyses will be performed by select AE category. Some analyses may also be repeated by subcategory of endocrine events.

Select AEs includes:

- Pulmonary toxicity
- Gastrointestinal toxicity (diarrhea or colitis)
- Endocrinopathies
- Hepatotoxicity (including asymptomatic LFT elevations)
- Renal toxicity
- Skin toxicity
- Neurological toxicity
- Hypersensitivity/infusion reactions

7.6.5.1 Incidence of Select AE

Select AEs (see Table 7.6-1) will be summarized by tumor type for each category/subcategory for all treated subjects.

- Overall summary of any select AEs by worst CTC grade (grade 1, 2, 3, 4, 5, unknown) presented by Category or Subcategory/PT.
- Overall summary of drug-related select AEs by worst CTC grade (grade 1, 2, 3, 4, 5, unknown) presented by Category or Subcategory/PT.
- Summary of frequency of unique select AEs

The analyses will be conducted using the 100-day or for a total of 26 weeks from first on-study treatment with nivolumab whichever is earliest safety window.

By-subject select AE listing will be provided.

7.6.6 Immune Modulating Medication

The percentage of subjects who received immune modulating concomitant medication for

- management of adverse event
- premedication
- other use
- any use
- management of drug-related select adverse event (any grade, grade 3-5) by select AE category/ subcategory
- management of IMAEs (any grade, grade 3-5) by IMAE category will be reported separately for each tumor group (percentages of treated subjects by medication class and generic term).

The following will be reported for each tumor group:

- The total medication treatment duration (excluding overlaps), duration of high dose of corticosteroid, initial dose of corticosteroid, and tapering duration (summary statistics)

The analysis will be conducted using the 100-day or for a total of 26 weeks from first on-study with nivolumab whichever is earliest safety window.

7.6.7 Immune Mediated Adverse Events

In order to further characterize AEs of special clinical interest analysis of immune-mediated AEs (IMAE) will be conducted. Immune-mediated AEs are specific events (or groups of PTs describing specific events) that include pneumonitis, diarrhea/colitis, hepatitis, nephritis/renal dysfunction, rash, endocrine (adrenal insufficiency, hypothyroidism/thyroiditis, hyperthyroidism,

diabetes mellitus, and hypophysitis), and other specific events, considered as potential immune mediated events by investigator, that meet the definition summarized below:

- those occurring within 100 days of the last dose or for a total of 26 weeks from first on-study treatment with nivolumab whichever is earliest
- regardless of causality,
- treated with immune-modulating medication (of note, endocrine Adverse events such as adrenal insufficiency, hypothyroidism/thyroiditis, hyperthyroidism, diabetes mellitus, and hypophysitis are considered IMAEs regardless of immune-modulating medication use, since endocrine drug reactions are often managed without immune-modulating medication).

For the most recent studies, the data collection for IMAE was modified to also collect data on investigator assessment of potential IMAE including evidence of immune mediated etiology. For these studies (which will be clearly identified as such in the study specific SAP), an additional criteria accounting for immune mediated etiology or immune mediated component is also to be considered:

- with no clear alternate etiology based on investigator assessment, or with an immune mediated component

The list of MedDRA preferred terms used to identify Immune-Mediated adverse events is revisited quarterly and updated accordingly. The preferred terms used for the selection at the time of the database lock by categories will be provided.

IMAEs will be summarized for each immune mediated category / PT using the 100 days of the last dose or for a total of 26 weeks from first on-study treatment with nivolumab whichever is earliest:

- Overall summary of AEs by worst CTC grade (grade 1, 2, 3, 4, 5, unknown) presented by immune mediate Category/ PT. This summary includes all AEs that are qualified for IMAE preferred terms list, without requirement of either usage of immune modulating medications or accounting for immune mediated etiology or immune mediated component. .
- Overall summaries of IMAEs by worst CTC grade [(grade 1, 2, 3, 4, 5, unknown) and (any grade, grade 3-4, grade 5)] where immune modulating medication was initiated presented by Category / PT
- Overall summaries of endocrine IMAEs by worst CTC grade [(grade 1, 2, 3, 4, 5, unknown) and (any grade, grade 3-4, grade 5)] presented by Category / PT.
- Overall summaries of serious IMAEs by worst CTC grade [(grade1, 2, 3, 4, 5, unknown)and (any grade, grade 3-4, grade 5)] where immune modulating medication was initiated presented by Category / PT.

- Overall summaries of endocrine serious IMAEs by worst CTC grade [(grade 1, 2, 3, 4, 5, unknown) and (any grade, grade 3-4, grade 5)] presented by Category / PT.
- Overall summaries of IMAEs leading to discontinuation by worst CTC grade [(grade 1, 2, 3, 4, 5, unknown) and (any grade, grade 3-4, grade 5)] where immune modulating medication was initiated presented by Category / PT.
- Overall summaries of endocrine IMAEs leading to discontinuation by worst CTC grade [(grade 1, 2, 3, 4, 5, unknown) and (any grade, grade 3-4, grade 5)] presented by Category / PT.
- Overall summaries of IMAEs leading to dose delay or reduction by worst CTC grade [(grade 1, 2, 3, 4, 5, unknown) and (any grade, grade 3-4, grade 5)] where immune modulating medication was initiated presented by Category / PT.
- Overall summaries of endocrine IMAEs leading to dose delay or reduction by worst CTC grade [(grade 1, 2, 3, 4, 5, unknown) and (any grade, grade 3-4, grade 5)] presented by Category / PT.
- Summaries of time to onset and time to resolution of IMAEs where immune modulating medication was initiated presented by Category.
- Summaries of time to onset and time to resolution of endocrine IMAEs presented by Category.

By-subject listing of IMAEs will be provided. By-subject listings of time to resolution for longest IMAEs cluster (any grade and grade 3-5 in separate summaries) will also be provided. For new studies which collect investigator assessment of potential IMAE data, a listing of Adverse Events Considered as Immune-Mediated Events per Investigator but not Qualified for Immune-Mediated Adverse Events Definition will also be provided.

In addition, for all nivolumab treated subjects who experienced at least one immune-mediated adverse event, the following data presentation will be provided:

- Summary of subjects who were re-challenged with nivolumab by immune-mediated adverse event category, with extended follow-up
- Summary of subjects who were re-challenged with nivolumab or ipilimumab by immune mediated adverse event category with extended follow-up

For these, re-challenge is considered to have occurred when last nivolumab and/or ipilimumab infusion was administered after the onset of an IMAE.

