2 SCHEDULE OF ACTIVITIES

Table 2-1: CA209887 Screening procedures and assessments

Procedure	Screening Visit	Notes
		Screening visit will occur within 28 days before start of nivolumab
Eligibility Assessments		
Informed Consent	X	
IVRS	X	An Interactive voice recognition system (IVRS) will be used to assign participant numbers.
Inclusion/Exclusion Criteria	X	
Medical History	X	Medical history will include smoking history, and comorbidities. Mutation status of EGFR and ALK will be collected if available. Additional biopsies for mutation status, if not previously tested, are not required.
Safety Assessments		
Physical Examination	X	Includes height, weight, and ECOG PS (Appendix 1). Full physical exam required at baseline.
Vital Signs	X	Temperature, BP, HR, RR. Obtain vital signs at screening visit and within 72 hours of first dose
Assessment of Signs and Symptoms	X	After obtaining Informed Consent, assess all signs and symptoms within 14 days of first dose, prior to study treatment initiation
Concomitant medications	X	Within 14 days of first dose
Laboratory Tests	X	Laboratory Tests performed locally within 14 days prior to first dose (unless otherwise specified): CBC with differential, serum chemistry (BUN or serum urea level, serum creatinine, sodium, potassium, calcium, magnesium, phosphate, chloride, and glucose), liver function tests (AST, ALT, total bilirubin, alkaline phosphatase, albumin, LDH). TSH, free T3, free T4 (within 28 days prior to first dose), hepatitis B surface antigen (HBsAg) and hepatitis C antibody (HCV Ab) or HCV RNA.
Pregnancy Test	X	Within 24 hours prior to first dose for WOCBP only (serum or urine at the site).

ALT = alanine aminotransferase, AST = aspartate aminotransferase; BP = blood pressure; BUN = blood urea nitrogen; CBC = complete blood count; ECOG = Eastern Cooperative Oncology Group; HR = heart rate; LDH = lactate dehydrogenase; NCI CTCAE = National Cancer Institute Common Terminology Criteria for AEs; RR = respiratory rate, TSH = thyroid stimulating hormone, T3 = triiodothyronine, T4 = thyroxine; WOCBP = Women of Childbearing Potential

Table 2-2: CA209887: On-Study Procedures and assessments

Procedure	Each Cycle (Every 2 weeks)	Notes
Safety Assessments		

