6.2 Exclusion Criteria

1) Medical Conditions

- a) Women who are pregnant or breastfeeding
- b) Women with a positive pregnancy test at enrollment or prior to administration of study medication
- c) Participants with untreated, symptomatic central nervous system (CNS) metastases.
- d) Participants with carcinomatous meningitis.
- e) Participants with active, known or suspected autoimmune disease. Participants with type I diabetes mellitus, hypothyroidism only requiring hormone replacement, skin disorders (such as vitiligo, psoriasis or alopecia) not requiring systemic treatment, or conditions not expected to recur in the absence of an external trigger are permitted to enroll

- f) Participants with a condition requiring systemic treatment with either corticosteroids (> 10 mg daily prednisone equivalent) or other immunosuppressive medications within 14 days of first dose of study drug. Inhaled or topical steroids, and adrenal replacement steroid doses > 10 mg daily prednisone equivalent, are permitted in the absence of active autoimmune disease.
- g) Other active malignancy requiring concurrent intervention.
- h) Participants with previous malignancies (except non-melanoma skin cancers, and the following in situ cancers: bladder, gastric, colon, endometrial, cervical/dysplasia, melanoma, or breast) are excluded unless a complete remission was achieved at least 2 years prior to study entry AND no additional therapy are ongoing and required during the study period with the exception of anti-estrogen/androgen therapy or bisphosphonates. Participants with other active malignancy requiring concurrent intervention are excluded.
- i) All toxicities attributed to prior anti-cancer therapy other than alopecia, fatigue, or peripheral neuropathy must have resolved to Grade 1 (NCI CTCAE version 4) or baseline before administration of study drug.
- j) Participants must have recovered from the effects of major surgery or significant traumatic injury at least 14 days before the first dose of study treatment.
- k) Known history of positive test for human immunodeficiency virus (HIV) or known acquired immunodeficiency syndrome (AIDS). NOTE: Testing for HIV must be performed at sites where mandated locally.

2) Prior/Concomitant Therapy

- a) Ongoing or planned administration of anti-cancer therapies other than those specified in this study

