- b) Use of corticosteroids or other immunosuppressive medications with exceptions detailed in the protocol consistent with nivolumab program.
- c) Treatment with any investigational agent within 14 days of first administration of study treatment

3) Physical and Laboratory Test Findings

- a) WBC < 2000/mm³
- b) Neutrophils < 1500/mm³
- c) Platelets < 100*10³/mm³
- d) Hemoglobin < 9.0 g/dL
- e) Serum creatinine > 1.5 x ULN or calculated creatinine clearance < 40 mL/min (using the Cockcroft-Gault formula)
- f) AST/ALT: > 3.0 x ULN
- g) Total bilirubin > 1.5 x ULN (except participants with Gilbert Syndrome who must have a total bilirubin level of < 3.0x ULN)
- h) Any positive test result for hepatitis B virus or hepatitis C virus indicating presence of virus, e.g. Hepatitis B surface antigen (HBsAg, Australia antigen) positive, or Hepatitis C antibody (anti-HCV) positive (except if HCV-RNA negative). Any serious or uncontrolled medical disorder or active infection with hepatitis that may be reactivated.

4) Allergies and Adverse Drug Reaction

- a) History of severe hypersensitivity reactions to other monoclonal antibodies.
- b) History of allergy or intolerance (unacceptable adverse event) to study drug components, or Polysorbate-80-containing infusions.
- c) Participants with history of life-threatening toxicity related to prior immune therapy (eg. anti-CTLA-4 or anti-PD-1/PD-L1 treatment or any other antibody or drug specifically targeting T-cell co-stimulation or immune checkpoint pathways) except those that are unlikely to re-occur with standard countermeasures (eg. Hormone replacement after adrenal crisis).

5) Other Exclusion Criteria

- a) Prisoners or participants who are involuntarily incarcerated. (Note: under certain specific circumstances a person who has been imprisoned may be included or permitted to continue as a participant. Strict conditions apply and Bristol-Myers Squibb approval is required.
- b) Participants who are compulsorily detained for treatment of either a psychiatric or physical (e.g., infectious disease) illness

Eligibility criteria for this study have been carefully considered to ensure the safety of the study participants and that the results of the study can be used. It is imperative that participants fully meet all eligibility criteria.

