6 STUDY PERIODS, TREATMENT REGIMENS AND POPULATIONS FOR ANALYSES

6.1 Study Periods

6.1.1 *Baseline Period*

Baseline evaluations or events will be defined as evaluations or events that occur before the date and time of the first dose of study treatment. Evaluations on the same date and time of the first dose of study treatment will be considered as baseline evaluations.

In cases where the time (onset time of event or evaluation time and dosing time) is missing or not collected, the following definitions will apply:

- Pre-treatment AEs will be defined as AEs with an onset date prior to but not including the day of the first dose of study treatment
- Baseline evaluations (e.g., laboratory tests and vital signs) will be defined as evaluations with a date on or prior to the day of first dose of study treatment

If there are multiple valid assessments, the assessment that is closest to day (and time if collected) of the first dose of study treatment will be used as the baseline in the analyses. If multiple assessments are collected at the same date (and time if collected), the assessment with the latest database entry date (and time if collected) will be considered as baseline.

6.1.2 *Post Baseline Period*

- On-treatment AEs will be defined as AEs with an onset date and time on or after the date and time of the first dose of study treatment (or with an onset date on or after the day of first dose of study treatment if time is not collected or is missing). For subjects who are off study treatment, AEs will be included if event occurred within a safety window of 100 days after the last dose of study treatment or for a total of 26 weeks from first on-study treatment with nivolumab, whichever is earliest. No subtracting rule will be applied when an AE occurs both pre-treatment and post-treatment with the same preferred term and grade.

- On-treatment evaluations (laboratory tests and vital signs) will be defined as evaluations taken after the day (and time, if collected and not missing) of first dose of study treatment. For subjects who are off study treatment, evaluations should be within a safety window of 100 days after the last dose of study treatment or for a total of 26 weeks from first on-study treatment with nivolumab, whichever is earliest.

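### Endocrine IMAE summaries in SAP 7.6.7 do not separate new onset from post-dose records of a condition that was already present at entry

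*SAP*

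**What the plan says.** Five parts of the plan bear on this point.

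- **IMAE definition (SAP 7.6.7).** Events in the listed categories qualify "regardless of causality" if they fall in the safety window and were treated with immune-modulating medication. Adrenal insufficiency, thyroid disorders, diabetes mellitus and hypophysitis are exempt from the medication condition: they "are considered IMAEs regardless of immune-modulating medication use".
- **Aetiology criterion (SAP 7.6.7).** Studies that collect the investigator's assessment add a further condition: "with no clear alternate etiology based on investigator assessment, or with an immune mediated component". The SAP of such a study is meant to identify it as one. The available text of this SAP does not say whether CA209887 is.
- **Period rules (SAP 6.1.2).** "On-treatment AEs will be defined as AEs with an onset date and time on or after the date and time of the first dose". The same paragraph adds: "No subtracting rule will be applied when an AE occurs both pre-treatment and post-treatment with the same preferred term and grade".
- **Eligibility (Protocol 6.2).** Criterion 1e lists as permitted "Participants with type I diabetes mellitus, hypothyroidism only requiring hormone replacement, skin disorders". Criterion 1f allows adrenal replacement steroids if there is no active autoimmune disease. Criterion 4c excludes a history of life-threatening toxicity from prior immune therapy, "except those that are unlikely to re-occur with standard countermeasures (eg. Hormone replacement after adrenal crisis".
- **Baseline data.** Protocol Table 2-1 collects comorbidities, serum glucose and "TSH, free T3, free T4 (within 28 days prior to first dose". SAP 7.3.4 codes medical history in MedDRA.

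**The concern.** The endocrine categories are the only named IMAE categories with neither a causality condition nor a treatment condition. They are also the categories in which the protocol knowingly admits participants who already have the disease. With same-term, same-grade subtraction switched off, the tables have no step that tells new toxicity from a further record of an old condition.

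This is a single-arm study meant to describe the safety profile in India, so no control group shows the background level. The affected outputs are the endocrine IMAE summaries in SAP 7.6.7: overall, serious, leading to discontinuation, leading to dose delay, and time to onset and resolution. The re-challenge summary is also affected. It counts a participant as re-challenged when the last infusion came after the onset of an IMAE, so someone with long-standing hypothyroidism who has one post-dose record and simply continues dosing would be included.

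**Working it through.** **1. Figures in the plan.** The documents give no expected rate for endocrine IMAEs, so there is no figure of theirs to reproduce on this point. The nearest ones are in SAP Section 5, and they reproduce. The exact binomial tail probabilities are 0.9867, 0.8412, 0.9744 and 0.8773, against the stated 99%, 84%, 97% and 88%. All 24 Clopper-Pearson intervals in Table 5-1 match to two decimals. Neither set bears on the definition.

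**2. Tracing one participant through the rules.** Take a participant who enters with replaced hypothyroidism (permitted by 1e).

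- *No post-dose AE record.* The onset rule in SAP 6.1.2 is not met, so nothing is counted.
- *Post-dose AE record.* Protocol Table 2-2 schedules thyroid tests every 6 weeks and chemistry, including glucose, every cycle. Protocol 9.2.6 sends a laboratory abnormality that needed specific corrective therapy to the AE page and prefers the clinical term. An abnormal TSH followed by corrective therapy can therefore become a post-dose hypothyroidism AE. Its onset is after first dose, causality is not asked, medication is not required, and the same term and grade before treatment does not remove it. It is counted.
- *Aetiology criterion.* If it applies, the investigator could name the known disease as a clear alternate cause and the event would drop out. If it does not, the event stays. Either way, the first summary listed in SAP 7.6.7 uses the preferred-term list alone and keeps it.

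**3. Size, on assumed inputs.** Let t be the new-onset endocrine IMAE rate, p the share entering with a permitted condition, and s the share of those with a post-dose AE record of it. None of the three is in the documents. The assumed values are t = 10%, p = 2% to 15% and s = 0% to 50%.

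Apparent rate = t(1 − p) + p[s + (1 − s)t] = t + p·s·(1 − t)

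| p | s | Calculation | Apparent rate |
|---|---|---|---|
| any | 0% | 0.10 + 0 | 10.0% |
| 2% | 25% | 0.10 + 0.02 × 0.25 × 0.90 | 10.45% |
| 5% | 50% | 0.10 + 0.05 × 0.50 × 0.90 | 12.25% |
| 10% | 50% | 0.10 + 0.10 × 0.50 × 0.90 | 14.5% |
| 15% | 50% | 0.10 + 0.15 × 0.50 × 0.90 | 16.75% (16.8%) |

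The top row of assumptions (p = 15%, s = 50%) with other values of t gives 0.05 + 0.075 × 0.95 = 12.1% for t = 5%, and 0.20 + 0.075 × 0.80 = 26.0% for t = 20%.

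**4. Scale.** The exact 95% interval for 10/100 is 4.9% to 17.6%, and for 15/100 it is 8.6% to 23.5%. In the RCC column, two such participants would move 3/30 (10.0%) to 5/30 (16.7%).

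**The case against.** The strongest reply is that the plan already has controls and that the effect may be nil.

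- **Onset rule.** A reader might infer that every participant with endocrine disease at entry becomes an endocrine IMAE. The documents do not support that. Onset must be on or after first dose, comorbidities go to medical history, pre-treatment occurrences go to a separate eCRF section (Protocol 9.2.1), and laboratory values become AEs only under the conditions of Protocol 9.2.6. This stands, and it limits the concern to conditions that are re-recorded.
- **Investigator assessment.** A reader might also infer that the aetiology criterion could not help, because type 1 diabetes or autoimmune thyroid disease has its own immune component. The documents do not say so, nor that the permitted hypothyroidism is autoimmune. Protocol 9.2 requires non-inflammatory explanations to be excluded and says supporting information is collected on the CRF, which points towards applying the criterion. Its status is unresolved rather than ineffective. SAP 7.6.7 also mentions events the investigator considers potentially immune-mediated, but it is unclear whether that phrase covers the endocrine list or only the other specific events.
- **Endpoints.** IMAEs are neither primary nor secondary (SAP 4.1, 4.2). Endocrine toxicity is a secondary endpoint through treatment-related select AEs, and that table in SAP 7.6.5.1 keeps its relatedness condition. This stands.
- **Exacerbation.** Protocol 9.2 accepts an event with another cause that induced autoimmunity made worse, so some records in participants with disease at entry are valid IMAEs. This stands and shapes the fix.
- **Listings and unseen text.** By-subject IMAE and medical-history listings would let a reader find these participants, though not from the tables. Protocol Appendix 6 is not in the available text and part of SAP 7.6.8 is redacted, so a recording rule for worsening of a pre-existing condition may exist and cannot be ruled out.

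**Conclusion.** The gap is real but narrow. As written, a post-dose AE record of an endocrine condition present at entry, even at unchanged grade, can enter the endocrine IMAE incidence, time-to-onset and re-challenge summaries, and those tables do not show it separately.

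The size cannot be derived from the documents. With t = 10%, the assumed ranges give an apparent rate of 10.0% to 16.8%. The result depends on the product of p and s, and is zero when stable disease is never re-recorded. A reader might expect time to onset to be shortened. That direction is not established, because a re-recorded event can start at any point in the window. The primary endpoint is untouched, and the drug-related select-AE table is not affected in the same way.

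This is a low-cost improvement to supportive safety tables.

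**What to change.** Change SAP 7.6.7 only.

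1. Keep the all-event endocrine IMAE rows. Add a split by whether the same condition was present at baseline, derived by a written rule from coded medical history, screening TSH, free T3 and free T4, and screening glucose. Give incidence and time to onset for new-onset events, with participants free of that condition at baseline as the denominator.
2. Show events in participants who had the condition at baseline in a separate row. Do not drop same-grade events: Protocol 9.2 allows exacerbation by induced autoimmunity, and no baseline grade is described for medical history against which to measure worsening.
3. State whether the aetiology criterion applies to CA209887, consistently with Protocol 9.2, and settle this before database lock.

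The cost is one derived baseline flag and additional table rows. No new assessments are needed. The drawback is small counts in the split rows, especially in RCC (n = 30).
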